### 3.2.2.2 EXPANSION COHORT

- Antitumor activity observed with Olaparib given in association with radiotherapy in terms of 6-month objective response, best response under treatment, best objective response under treatment, 1-year PFS and 1-year OS, as defined for the dose escalation part.
- Toxicity graded using the common toxicity criteria from the NCI v4.03.
- PK measurements expressed as AUC, half-life and concentration peak for Olaparib.
- Pharmacodynamics (translational research): Prognostic markers of anti-tumor activity of Olaparib given with concomitant radiotherapy will be investigated.

The previous criteria will be analyzed in the same way as for the dose escalation part (see section 3.2.2.1).

### 3.3 ADDITIONAL ANALYSIS

In addition to the above endpoints, further analyses will be conducted to assess the potential impact of COVID-19 on patient care.

Criteria	eFORM variable	Control
Covid-19 infection	COV_INF INF_COV	INF_COV EQ 1

The number of patients infected with covid-19 will be reported. In case of high numbers, the previous endpoints could be evaluated among the population of infected patients for comparison (no formal test).

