3.4.1. Treatment scheme and DLT observation period

- Olaparib will be given orally, continuously, twice a day, as appropriate for assigned dose level, from D1 to the end of radiotherapy. Olaparib will be started one week before the start of radiotherapy and will be continued until the last day of radiotherapy. Beyond this period, Olaparib could be continued until progression, at the investigator's discretion and sponsor approval.
- Radiotherapy consists of fractionated focal irradiation at a dose of 1.8 Grays (Gy) per fraction given once daily five days per week (Monday through Friday), for a total dose of 59.4 Gy (i.e 33 fractions). Radiotherapy starts at D8.
- The DLT observation period is defined as the first day of Olaparib intake and up to 6 weeks after the end of radiotherapy (13.5 weeks).

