In case of surgery, post surgery complications must be reported during 12 months after the surgery unless start of a new anti-tumor therapy.

5.7.FOLLOW-UP AFTER END-OF-TREATMENT VISIT

- Each patient will be followed-up for 12 months after inclusion.
- The date and reason of the study discontinuation will be recorded on the patient's CRF (see Section 5.2).
- After treatment discontinuation, patients will be followed every 3 months until death or until the end of the follow-up period, whichever occurs first.
- Patients who withdraw consent will not be followed with any study procedures.

All AEs (including SAEs) suspected to be treatment-related (Olaparib and/or radiotherapy) or research-related will be followed-up until the events or their sequelae resolve or stabilize at a level acceptable to the Investigator and the Sponsor.

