### 3.2.1.2 EXPANSION COHORT

6-month non progression, defined as complete (CR) or partial response (PR) at 6 months confirmed  $\geq 4$  weeks after initial documentation, or stable disease more than 24 weeks (RECIST v1.1, as determined by investigator review of tumor assessments).

For the expansion cohort, radiological data will be centrally reviewed. The primary analysis will be based on reviewed data.

Criteria	eFORM variable	Control
6-month non progression	TUM_CYC (TUMOR ASSESSMENT) DT_MEAC (date of measurement) ME1L_ME5L (measures of lesions) SUM_TL (largest diameters) EVA1LNM_EVA5LNM (non-measurable lesions eval) RES_TL, RES_NTL (target and non-target lesions) OV_RESP (overall response) CR=1, PR=2, SD=3 TRT_OLA DT_S10 (D1 Olaparib)	DT_S10 filled in ME1L_ME5L (filled in if needed) SUM_TL filled in EVA1LNM_EVA5LNM (filled in if needed) RES_TL, RES_NTL (filled in) and check recist1.1 criteria  check for each patient (( DT_MEAC-DT_S10 $\geq 6$ ) and OV_RESP =(1 or 2 or 3)) Count number of non-progression case

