### 3.2.2 SECONDARY ENDPOINT

#### 3.2.2.1 DOSE ESCALATION PART

Antitumor activity observed with Olaparib given in association with radiotherapy in terms of

- 6-month non progression, defined as complete (CR) or partial response (PR) at 6 months confirmed  $\geq 4$  weeks after initial documentation, or stable disease more than 24 weeks (RECIST v1.1, as determined by investigator review of tumor assessments)
- 6-month objective response, defined as CR or PR at 6 months confirmed  $\geq 4$  weeks after initial documentation, as determined by investigator review of tumor assessments using RECIST v1.1
- Best objective response under treatment is defined as complete (CR) and partial response (PR) recorded from the start of study treatment until the treatment with confirmation  $\geq 4$  weeks after initial documentation, as per RECIST 1.1. Objective response under treatment is determined once all the data for the patient is known.
- Best response under treatment is defined as the best response (CR, PR, SD) as per RECIST 1.1 recorded from the start of the study treatment until the end of treatment taking into account any requirement for confirmation as per RECIST v1.1 criteria. It is determined once all the data for the patient is known.
- 1-year Progression-free survival (PFS): PFS is defined as the time from study treatment initiation to the first occurrence of disease progression or death (of any cause), whichever occurs first.

- 1-year Overall Survival (OS): OS is defined as the time from study treatment initiation to death (of any cause).
- Functional assessment
  - Graded using the Musculoskeletal Tumour Society Rating Scale (Enneking, Modification of the system for functional evaluation in the surgical management of musculoskeletal tumours. In: Enneking WF, ed. Limb Salvage in Musculoskeletal Oncology. New York, NY: Churchill Livingstone, 1987:626A39.
  - MSTS will be completed by the radiotherapist at baseline and at the end of radiotherapy treatment.
  - The MSTS score is calculated from 6 functional criteria.
    - Three subjective criteria are common to the upper and lower limbs: pain, function, emotional acceptance of the surgical procedure (psychological acceptance).
    - The other three are objective criteria:
      - For the lower limb: support, walking and gait.
      - For the upper limb: the position relative to shoulder, dexterity, muscle strength

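### Run as written, the optional COVID-19 comparison in SAP 3.3 would build immortal-time bias into OS, PFS and 6-month non-progression and could mask harm

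*SAP*

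**What the plan says.** SAP 3.3 gives its purpose as follows: "further analyses will be conducted to assess the potential impact of COVID-19 on patient care". The only firm commitment is a count of infected patients. The section then adds that, if the numbers are high, "the previous endpoints could be evaluated among the population of infected patients for comparison (no formal test". The infected group is selected by a single condition, the indicator INF_COV equal to 1. No infection date, time window, threshold for the trigger or comparator (never-infected patients, or all patients) is given.

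The endpoints referred to are defined in SAP 3.2:

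- **OS** (SAP 3.2.2.1): "OS is defined as the time from study treatment initiation to death (of any cause".
- **PFS** (SAP 3.2.2.1): "PFS is defined as the time from study treatment initiation to the first occurrence of disease progression or death (of any cause". For both PFS and OS, the programming rules subtract the olaparib start date.
- **6-month non-progression** (SAP 3.2.1.2): confirmed CR or PR at 6 months, "or stable disease more than 24 weeks". This is a status at a fixed time after treatment start.

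Protocol 5.7 sets the observation time: "Each patient will be followed-up for 12 months after inclusion". Visits continue after treatment stops, so an infection could be recorded at any time in that year, including after progression.

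SAP 3.1.1 makes every analysis descriptive. The lists of data listings and tables in SAP 4.1 and 4.2 contain no COVID-19 item. SAP 4.2.7 does tabulate treatment adaptations (Table 7.1), delays (Table 7.3) and interruptions (Table 7.4) for olaparib and radiotherapy, with reasons.

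**The concern.** An infection caught during the study is a post-baseline event, and a patient can enter the infected group only by being alive when it happens. Early deaths therefore fall mostly into the other group, whatever infection does. Since the OS clock starts at treatment and not at infection, the time before infection is counted as survival of the infected group.

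The same applies to PFS and 6-month non-progression. For example, a patient infected in month 8 was necessarily alive at month 6. If only infections before progression are recorded, that patient was also necessarily progression-free at month 6.

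At stake is a misleading descriptive result: infected patients may appear to do as well as or better than others when infection made no difference, or even when it did harm. The comparison is also an indirect route to the stated aim. Impact on care shows up as missed or late scans and treatment interruptions, which can affect patients who were never infected. Because SAP 3.1.1 does not impute missing data, a missed week-24 scan bears directly on the expansion cohort's primary endpoint.

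**Working it through.** SAP 3.3 states no rate, effect or sample size, so there is no plan figure to reproduce. The check asks what the grouping rule produces when the truth is known.

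**Inputs from the documents.** The clock starts at treatment (SAP 3.2.2.1), follow-up is 12 months (Protocol 5.7), the group is defined by an undated flag (SAP 3.3), and the trial has 26 + 15 = 41 patients.

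**Assumed inputs (none is in the documents).** 1-year OS is S and 12-month infection risk in the absence of death is I. Hazards are constant, infection is independent of death risk, and the comparator is never-infected patients.

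**Step 1. Closed form, no effect of infection.** With death hazard L = −ln S and infection hazard h = −ln(1 − I):

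- P(infected while alive within the year) = h/(h + L) × (1 − exp(−(h + L)))
- P(alive at 1 year | infected) = S × I / P(infected)
- P(alive at 1 year | never infected) = S × (1 − I) / (1 − P(infected))

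For S = 0.65 and I = 0.20, L = 0.431 and h = 0.223:

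- P(infected) = 0.223/0.654 × (1 − 0.52) = 0.164
- Infected: 0.13/0.164 = 79%
- Never infected: 0.52/0.836 = 62%

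The gap is 17 points where the truth is zero. Against all patients it would be 79% against 65%, or 14 points.

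**Step 2. Range.** For S from 0.5 to 0.8 and I from 0.1 to 0.4, the gap runs from 10 points (S = 0.8, I = 0.1: 89% against 79%) to 25 points (S = 0.5, I = 0.4: 67% against 43%).

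**Step 3. Simulation (2,000,000 patients per scenario).** Over 1-year OS of 50–90% and infection risk of 10–30%, with no true effect, the flag gives a death-rate ratio of 0.44–0.49 (truth 1.0). The OS gap runs from 5 points (94.8% against 89.5%) to 23 points (67.9% against 44.9%). Treating infection as a time-dependent status returns 0.98–1.01, so the distortion comes from the grouping rule.

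**Step 4. When infection does harm (OS 65% without infection, infection risk 20%).**

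| True hazard ratio after infection | 1-year OS by flag: infected vs not | Death-rate ratio by flag | 6-month landmark, OS to month 12: infected vs not |
|---|---|---|---|
| 1 | 79.3% vs 62.2% | 0.47 | 80.5% vs 80.7% |
| 2 | 63.9% vs 62.2% | 0.87 | 64.9% vs 79.7% |
| 2.5 | 57.8% vs 62.2% | 1.05 | 58.4% vs 79.3% |
| 3 | 52.5% vs 62.2% | 1.22 | 52.7% vs 79.1% |

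A doubled hazard is hidden and a tripled one looks like 1.22. The landmark shows no difference when there is none and shows the harm when there is.

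**Step 5. 6-month non-progression, no effect of infection.** With assumed median time to progression of 6–12 months, OS 65% and infection risk 20%, the infected group gains 8 to 12 points if infections after progression count. It gains 23 to 34 points if only infections before progression are captured.

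**Step 6. Precision.** If 8 of 41 patients were infected and 6 of the 8 were non-progressors, the exact 95% interval would be 35% to 97%.

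**What the model leaves out.** It gives every patient the same chance of infection. Protocol 5.1 plans first inclusion in October 2016 and about 56 months of enrolment. A patient included at the start would finish 12 months in October 2017, before COVID-19 existed. Early patients are also those at the lower dose levels, and the expansion cohort comes last. Infection status is thus tied to calendar period, dose level and cohort, and this could add to or offset the bias.

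**The case against.** The strongest reply is that the section is optional, descriptive and inconsequential: the endpoints may be compared only if numbers are high, without a test, in at most 41 patients. That stands as an argument about priority. It does not remove the bias, because in a wholly descriptive plan the rates and Kaplan-Meier curves are the result. A trigger based on the number infected is ordinary feasibility wording and not itself a source of bias; it only needs a threshold.

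Several stronger readings are tempting but not supported:

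- *That the SAP commits to comparing infected with never-infected patients.* It says only that this could be done, and it names no comparator.
- *That infection is always acquired during follow-up.* The flag has no window, and an infection before treatment start carries no immortal time. The selection rule is undated, but the data may not be: an infection recorded as an adverse event would have a date (SAP 3.2.1.1).
- *That infected patients would look better purely because of this bias.* Step 4 shows the direction reversing once the true hazard ratio reaches 2.5, and differences in calendar period and cohort leave the net direction unknown.
- *That every endpoint is affected alike.* DLTs are counted over a window of "up to 6 weeks after the end of radiotherapy (13.5 weeks" (Protocol 3.4.1), and neither DLT nor PK depends on survival as OS does.
- *That the effect on treatment goes untabulated.* Tables 7.1, 7.3 and 7.4 cover adaptations, delays and interruptions with reasons, and Datalisting 1.2 lists protocol deviations by patient. What is missing is COVID-19 as a named reason and a table of missed or late tumour assessments.

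**Conclusion.** The point holds conditionally. If the optional comparison is made with the flag as defined, it carries immortal-time bias in favour of patients infected after treatment start, for OS, PFS and 6-month non-progression, and it can attenuate or hide real harm. Nothing in the protocol or SAP removes this.

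The 17-point gap in the central example illustrates the mechanism and is not a forecast for this trial. It rests on assumed survival and infection rates, constant hazards, equal opportunity for infection and a never-infected comparator.

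Priority is low. The DLT analysis, the MTD/RP2D decision and the Gehan rule do not depend on this section.

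**What to change.** Preferred change to SAP 3.3: delete the comparison of endpoints by infection status. Keep the count of infected patients and add a listing with infection date, treatment start date, dose level and cohort.

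If a comparison is kept, the SAP should:

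- name the comparator and the minimum number infected that triggers it;
- fix a landmark in advance and compare patients infected before it with those not infected by it, among patients event-free at that time, counting outcomes only afterwards;
- for 6-month non-progression, place the landmark before the 6-month assessment (the week-12 MRI is one candidate);
- state that the comparison is confounded by calendar period, dose level and cohort.

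To serve the stated aim, add COVID-19 as a reason in Tables 7.1, 7.3 and 7.4, and add one count of tumour assessments missed or late because of COVID-19, whether or not the patient was infected.

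The cost is a small SAP edit, one reason category and one short table. The infection date must be available. A landmark also discards patients with earlier events and treats later infections as uninfected. With few infected patients it would be imprecise, which is why deletion is the simpler choice.

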## 4 APPENDICES

### 4.1 LIST OF DATALISTING

#### 4.1.1 INCLUSION FORM

Datalisting 1.1. Demographic characteristics: patient's number, patient's code, investigator center, date of birth, date of inclusion, sex, signed and dated written informed consent, dose level

Datalisting 1.2. Major and minor protocol deviations by patient

#### 4.1.2 DRUG DELIVERY

Datalisting 2.1. Treatment up-to-date: treatment continuation, dose modification.

Datalisting 2.2. Olaparib: start date 1, stop date 1, start date 2, stop date 2, therapy change 2 , reason for change 2, start date 3, stop date 3, therapy change 3 , reason for change 3, start date 4, stop date 4, therapy change 4 , reason for change 4, start date 5, stop date 5, therapy change 5 , reason for change 5

Datalisting 2.3. Radiotherapy : start and end dates, cumulative dose, number of fractions, therapy change

#### 4.1.3 DOSE-LIMITING TOXICITY

Datalisting 3.1. Date of Cycle 1 Day 1, Dose of Olaparib, Date of last intake, Date of the event, imputability, grade, another DLT

#### 4.1.4 END OF TREATMENT

Datalisting 4.1. End of treatment: start and end dates of treatment, status, reason for the end of the treatment, date of progression, type of progression

#### 4.1.5 ADVERSE EVENT (if required)

Datalisting 5.1. Adverse event, date of event, SOC, initial intensity, maximum intensity, treatment modification, imputability, date of the end or death, treatment introduced, concomitant treatment

#### **4.1.6 SERIOUS ADVERSE EVENT**

Datalisting 6.1. Serious adverse event, date of event, SAE start date, SOC, initial intensity, maximum intensity, treatment modification, imputability, date of the end or death, treatment introduced, concomitant treatment

#### **4.1.7 END OF STUDY**

Datalisting 7.1. End date, Main reason, consent withdrawn, patient is lost to follow-up, death and cause

### **4.2 LIST OF TABLES**

#### **4.2.1 STUDY OVERVIEW**

- Table 1.1. First and last consent date, date of last end study
- Table 1.2. Number of patients included (by center)
- Table 1.4. Number of patients registered, treated, eligible, evaluable for safety, evaluable for efficacy by dose level
- Table 1.4.1 : Untreated patients
- Table 1.4.2 : Patients unevaluable for safety
- Table 1.4.3 : Patients unevaluable for efficacy
- Table 1.5. Final treatment work-up: number of discontinuation and reasons
- Table 1.6. Final trial work-up: status at last contact

#### **4.2.2 PATIENT CHARACTERISTICS AT BASELINE**

- Table 2.1. Demographic characteristics at baseline
- Table 2.2. Pregnancy and female reproductive status
- Table 2.3. General medical/clinical conditions at baseline
- Table 2.4 Description of medical and surgical history
  - Table 2.4.1 Medical and surgical history (Y/N) at baseline
  - Table 2.4.2 Medical and surgical history (pathology) at baseline
  - Table 2.4.3. Ongoing concomitant treatments at baseline
- Table 2.5. Descriptive statistics for hematological parameters at baseline
- Table 2.6. Descriptive statistics for biochemical parameters at baseline
- Table 2.7. Descriptive statistics for coagulation parameters at baseline
- Table 2.6. Descriptive statistics for serological parameters at baseline
- Table 2.6. Descriptive statistics for urinalysis parameters at baseline

#### **4.2.3 TUMOR CHARACTERISTICS AT BASELINE**

- Table 3.1. Description of disease diagnosis

- Table 3.2. Description of disease status
- Table 3.3. Description of Anatomic location
- Table 3.4. Description of Grade
- Table 3.5. Description of Metastasis (Y/N)
- Table 3.6. Description of sites of Metastasis
- Table 3.7. Description of previous treatment

#### **4.2.4 TUMOR ASSESSMENT AT BASELINE**

- Table 4.1. Description of measurable lesions
  - Table 4.1.1. Description of number of measurable lesions
  - Table 4.1.2. Description of lesion site and localization
  - Table 4.1.3. Description of lesion measures (mean, min, max, sum of largest diameters)
- Table 4.2. Description of non-measurable lesions
  - Table 4.2.1. Description of number of non-measurable lesions
  - Table 4.2.2. Description of lesion site and localization

#### **4.2.5 DRUG DELIVERY**

- Table 5.1. Dose levels: Number of patients
- Table 5.2. OLAPARIB: Frequency of delivered weeks by dose level
- Table 5.2.1. Delivery of OLAPARIB : frequency of delivered weeks
- Table 5.2.2. Delivery of OLAPARIB: number of patients
- Table 5.3. Description of Cumulative dose of OLAPARIB by dose level

#### **4.2.6 RADIOTHERAPY**

- Table 6.1. Description of Cumulative dose of Grays by dose level
- Table 6.2. Description of Cumulative number of fractions by dose level

#### **4.2.7 TREATMENT MODIFICATION**

- Table 7.1. Dose adaptations: frequency of adapted patients by dose level
- Table 7.1.1. OLAPARIB adaptation: frequency of adapted cycles, patients by dose level and reasons
- Table 7.1.2. GRAYS DOSE adaptation: frequency of adapted cycles, patients by dose level and reasons
- Table 7.3. Reasons of delayed administration by dose level: description of reason and others.
- Table 7.3.a. Delayed administration : frequency of delayed patients by dose level for OLAPARIB

- Table 7.3.b. Delayed administration : frequency of delayed patients by dose level for GRAYS DOSE
- Table 7.4. Reasons of interrupted administration by dose level :
- Table 7.4.1. Interrupted administration : frequency of interrupted weeks by dose level
- Table 7.4.2. Interrupted administration : frequency of interrupted patients by dose level

#### **4.2.8 END OF TREATMENT**

- Table 8.1. Status at end of treatment
- Table 8.2. Reasons for end of treatment

#### **4.2.9 DOSE-LIMITING TOXICITIES**

- Table 9.1. Dose-limiting toxicities by dose level
- Table 9.2. Any grade  $\geq 3$  musculoskeletal or cutaneous toxicity within the field of radiation [ Occurring at a radiotherapy dose  $< 30\text{Gy}$  /Occuring at a radiotherapy dose  $\geq 30\text{Gy}$  and without regress to a grade  $\leq 2$  in a time limit of 4 weeks] by dose level
- Table 9.3. Any non-hematological toxicity  $\geq$  grade 3 (except for nausea, vomiting, fatigue, alopecia and fever) by dose level
- Table 9.4. Laboratory abnormality  $\geq$  grade 3 lasting  $> 5$  days (except for hyperglycaemia and changes in serum electrolytes/enzymes without clinical impact) by dose level
- Table 9.5. Febrile neutropenia (absolute neutrophil count [ANC]  $< 1.0 \times 10^9/\text{L}$  and fever  $\geq 38.5^\circ\text{C}$ ) and/or documented infection with ANC  $< 1.0 \times 10^9/\text{L}$  by dose level
- Table 9.6. Grade 4 neutropenia (absolute neutrophil count  $< 500$ ) lasting  $\geq 7$  days by dose level
- Table 9.7. Grade 4 thrombocytopenia or bleeding requiring a platelet transfusion by dose level
- Table 9.8. Any other grade  $\geq 4$  by dose level
- Table 9.9. If needed listing of other DLT by dose level

#### **4.2.10 SAFETY: ADVERSE EVENTS**

- Table 10.1 Adverse events by patient
  - Table 10.1.1 : Number of patient with at least one AE
  - Table 10.1.2 : Number of patient with AE by SOC and NCI terms
  - Table 10.1.2 : Number of patient with AE by grade
- Table 10.2 Adverse events by term
  - Table 10.2.1 : Number of adverse events by SOC and NCI terms
  - Table 10.2.2 : Number of adverse events by grade

#### **4.2.11 EFFICACY: Response, Progression and Survival**

- Table 14.1. Frequency distribution of objective response on population evaluable for efficacy
- Table 14.2. Frequency distribution of 6-month non-progression on population evaluable for efficacy

- Table 14.3. Frequency distribution of progression at one year on population evaluable for efficacy
- Table 14.4. Frequency distribution of deaths at one year on population evaluable for efficacy
- Table 14.5. Median follow-up time on population evaluable for efficacy– Life table
- Table 14.6. Median progression-free survival on population evaluable for efficacy – Life table
- Table 14.7. Median overall survival on population evaluable for efficacy – Life table

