10.2. DEFINITION OF STUDY POPULATIONS

Dose escalation part

- Population assessable for DLT assessment :
 - Patients assessable for the DLT assessment must fulfill all the following criteria:
 - Completed the DLT assessment period
 - Received concomitantly at least seven consecutive days of Olaparib and radiotherapy treatment (any dose) at least once.
 - Unless they develop a DLT, the following patients will not be included in the population assessable for DLT :
 - Patients who did not receive radiotherapy
 - Patients who did not receive nor Olaparib;
 - Patients who did not complete the full DLT evaluation period and goes off-treatment for reasons other than toxicity;

These patients will be replaced to reach the sample size requirement for dose escalation study.

- Safety population: patients who received radiotherapy or olaparib, at least once, irrespective of the dose. .

Expansion cohort

- Eligible population: All patients included without major violation of eligibility criteria.
- Population eligible and assessable for the primary endpoint : patients who fulfill all criteria below:
 - Eligible patients
 - Received concomitantly at least seven consecutive days of Olaparib and radiotherapy treatment (any dose) at least once.
 - at least one disease measurement recorded not less than eight weeks after treatment onset.

The following patients will also be included in the population evaluable for efficacy; they will be considered as failures for the primary endpoint (i.e. progressive disease at 6 months) and not be replaced in the efficacy analysis:

- Eligible patients withdrawn due to drug-related toxicity without any tumor assessments after the start of study treatment.
- Eligible patients withdrawn due to significant clinical deterioration of unknown reason, hypersensitivity reactions, or unrelated AEs without any tumor assessments after the start of study treatment.
- ***Replacement of patients: patients who do not comply with the definition of the population "eligible and assessable for the primary endpoint" will be replaced to reach the sample size requirement for expansion cohort.***
- Safety population: patients who receive at least one administration of Olaparib, or radiotherapy treatment at least once.

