## 2.1.2 EXPANSION COHORT

- Eligible population: All patients included without major violation of eligibility criteria.
- Population eligible and assessable for the primary endpoint : patients who fulfill all criteria below:
  - Eligible patients
  - Received concomitantly at least seven consecutive days of Olaparib and radiotherapy treatment (any dose) at least once .
  - at least one disease measurement recorded not less than eight weeks after treatment onset.

The following patients will also be included in the population evaluable for efficacy; they will be considered as failures for the primary endpoint (i.e. progressive disease at 6 months) and not be replaced in the efficacy analysis:

- Eligible patients withdrawn due to drug-related toxicity without any tumor assessments after the start of study treatment.
- Eligible patients withdrawn due to significant clinical deterioration of unknown reason, hypersensitivity reactions, or unrelated AEs without any tumor assessments after the start of study treatment.
- ***Replacement of patients: patients who do not comply with the definition of the population "eligible and assessable for the primary endpoint" will be replaced to reach the sample size requirement for expansion cohort.***
- Safety population: patients who receive at least one administration of Olaparib, or radiotherapy treatment at least once.

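### Expansion-cohort PFS and OS start at first treatment but are limited to a set that generally needs a scan at week 8 or later, so early deaths can drop out and survival can look too good

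*SAP*

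**What the plan says.** SAP 4.2.11 lists "Median progression-free survival on population evaluable for efficacy" (Table 14.6) and "Median overall survival on population evaluable for efficacy" (Table 14.7). Tables 14.3 to 14.5, on one-year progression, one-year deaths and median follow-up, carry the same restriction. SAP 4.3 lists Kaplan-Meier curves for PFS and OS without naming a population.

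For the expansion cohort, Protocol 10.2 and SAP 2.1.2 define one efficacy set, headed "Population eligible and assessable for the primary endpoint". It needs eligibility, seven consecutive days of combined treatment, and "at least one disease measurement recorded not less than eight weeks after treatment onset". Patients who do not meet the definition are replaced. Some patients without scans are kept: "The following patients will also be included in the population evaluable for efficacy; they will be considered as failures for the primary endpoint". There are two such groups, both limited to patients never scanned once treatment had begun:
- The first covers those taken off because of toxicity attributed to the drug.
- The second is worded as "Eligible patients withdrawn due to significant clinical deterioration of unknown reason, hypersensitivity reactions, or unrelated AEs without any tumor assessments".

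On timing, SAP 3.2.2.1 says "OS is defined as the time from study treatment initiation to death (of any cause"), and PFS has the same origin. The derivations in that section subtract the olaparib start date from the event date. They contain no landmark or delayed entry.

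For dose escalation, Protocol 10.2 and SAP 2.1.1 define a DLT-assessable set and a safety set but no efficacy-evaluable set, although PFS and OS are secondary endpoints there too.

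**The concern.** Entry to the survival analysis depends partly on something that happens after time zero. A patient who dies in week 5 cannot have a measurement at week 8. Unless one of the two retained groups applies, that death leaves both numerator and denominator, and a replacement patient takes the place. Removing early deaths can move an OS curve only upward. For PFS the same applies to early progressors who are never scanned again.

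A condition of this kind is defensible for a 6-month response-type endpoint, which cannot be judged without imaging. OS needs no scan at all, and PFS needs none for a patient to enter the risk set. At stake are the one-year rates and medians of two secondary endpoints.

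**Working it through.** **1. The plan's own figure.** The documents assume no PFS or OS value for this trial. The one number attached to this set is 14 assessable patients (Gehan first stage, 20% rate, 5% error): 0.8^13 = 0.0550 and 0.8^14 = 0.0440, so 14 reproduces. It is not in dispute.

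**2. Who can fall out, applying SAP 2.1.2 as written.**
- *Death from known sarcoma at week 5, no scan.* There is no measurement at 8 weeks or later, and the loss is neither drug toxicity, hypersensitivity, an unrelated AE nor deterioration of unknown reason. The patient is outside the set and replaced.
- *Metastatic patient progressing on the first CT.* In the schedule of assessments, as its columns read in the extracted text, this CT sits in the W8 column, headed D50. That is 49 days after D1, or 7 weeks, so the scan is too early to qualify. Because the patient has had an assessment, neither retained group applies. Protocol 5.6 waives end-of-treatment imaging after confirmed progression. Without a later scan the patient is outside the set. Protocol Appendix 3, by contrast, counts patients who progress before the end of cycle 1 as evaluable for response.
- *Withdrawal for drug-related toxicity at week 4, no scan.* Kept.
- *Progression at week 6, scanned again at week 12.* Kept, with the early PFS event counted.

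**3. Size at the only survival rates in the documents.** Protocol 1.1 cites a radiotherapy cohort with 5-year OS of 35% and disease-free survival (DFS) of 24%. Assume a constant hazard and use DFS as a proxy for PFS. Let L = 8 weeks = 56/30.4375 = 1.84 months, and let f be the share of early events that is excluded. The reported 1-year rate is then

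S(12) / [1 − f × (1 − S(L))].

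- OS: S(12) = 0.35^(12/60) = 0.811; S(L) = 0.35^(1.84/60) = 0.968.
  - f = 1: 0.811/0.968 = 0.837 (+2.7 points)
  - f = 0.5: 0.811/0.984 = 0.824 (+1.3 points)
- PFS proxy: S(12) = 0.24^(12/60) = 0.752; S(L) = 0.24^(1.84/60) = 0.957.
  - f = 1: 0.785 (+3.4 points)
  - f = 0.5: 0.768 (+1.6 points)

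In 15 patients the expected number of deaths before week 8 is 15 × 0.032 = 0.48, and the chance of at least one is 1 − 0.968^15 = 38%.

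**4. Size at assumed, less favourable rates.** These 1-year rates are assumptions found in neither document. With f = 1 the reported rate is S^(1 − 8/52.18):

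| Endpoint | True 1-year rate | Reported | Shift (points) |
|---|---|---|---|
| OS | 70% | 73.9% | +3.9 |
| OS | 60% | 64.9% | +4.9 |
| PFS | 40% | 46.0% | +6.0 |
| PFS | 24% | 29.9% | +5.9 |

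These are upper bounds for a cut at week 8, because the retained groups and later scans keep some early events in.

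**5. Sensitivity to the cut.** For non-metastatic patients the first scheduled MRI is at week 12 (Protocol 5.5). If that were the first qualifying scan, L = 2.76 months and the f = 1 shifts at the cited cohort's rates would be +4.0 points (OS, 0.811 to 0.851) and +5.1 points (PFS proxy, 0.752 to 0.803).

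**6. In counts.** With 15 treated and 5 deaths in the year, 1-year OS is 10/15 = 66.7%. Leaving out one early death gives 10/14 = 71.4%, ignoring replacement.

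**The case against.** The case on the other side is substantial.

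- **The retained groups are broad.** They keep most losses for reasons other than known disease. A reader might infer that every early failure, toxic deaths included, is removed. The text does not support that: withdrawals for drug-related toxicity without a scan stay in. What remains unclear is whether a death counts as a withdrawal, and how toxicity from radiotherapy alone is classed.
- **PFS is not strictly immortal for 8 weeks.** Early progressors with a later scan remain. Non-metastatic patients have no scheduled scan before week 12, so few of their progressions can be dated before week 8. A constant hazard therefore probably overstates the early PFS loss.
- **Early deaths should be few.** Inclusion requires a life expectancy of at least 6 months, which points to the low end for OS.
- **No protocol rule is broken.** A reader might infer that the SAP contradicts a protocol rule to analyse every treated patient. The protocol fixes the time origin but names no survival population, so this is an analysis choice.
- **Escalation is not shown to share the bias.** The 8-week rule is written only for the expansion cohort. Carrying the immortal-time argument over to escalation would go beyond the text.
- **The consequence is limited.** Analyses are descriptive, the go rule rests on non-progression, and no comparison of PFS or OS with radiotherapy alone is planned. The exact 95% interval for 10/15 is 38% to 88%, far wider than any shift above. Exclusions would show in Tables 1.4.3 and 1.6, Datalisting 7.1 and the flow chart.

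All of this narrows the scope and size. None of it restores a patient lost to known disease before week 8, and visible exclusions do not correct the printed median.

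**Conclusion.** The point holds for the expansion cohort in limited form. As written, Tables 14.3 to 14.7 can drop patients who die or progress from known disease before week 8, or whose only scan precedes it, while the clock starts at treatment. OS and PFS can then be too high.

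The amount is undocumented and starts at zero. With a week-8 cut and a constant hazard, the cited cohort's rates give +1.3 to +2.7 points for 1-year OS and +1.6 to +3.4 for the PFS proxy, for half and for all early events excluded. Assumed 1-year OS of 60–70% gives at most about 4 to 5 points, and assumed 1-year PFS of 24–40% at most about 6. The ceiling rises if the week-12 MRI is the first qualifying scan.

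For dose escalation the defect is an undefined population: the tables cannot be programmed there as written. Since the endpoints are secondary and descriptive, this should be corrected before programming, but it does not threaten the trial's main conclusions.

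**What to change.** In SAP 4.2.11 and 4.3, run Tables 14.3 to 14.7 and the PFS and OS Kaplan-Meier figures on all patients who started study treatment, that is, the safety population of each part.

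Two programming details need settling:
- The flag ELI_SAF is coded only in the escalation section (2.1.1). Extend it to the expansion cohort, whose safety population is already defined in words in 2.1.2.
- Set time zero at the first dose of any study treatment. The present code uses the olaparib start date, which leaves a patient given radiotherapy alone without a start.

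If wanted, add eligible treated patients as a sensitivity analysis. Keep the assessable set for response Tables 14.1 and 14.2 only, and state which set those tables use in the escalation part.

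The cost is SAP wording and one population flag, with no new data. The downside is slightly less favourable survival figures and a different N from the response tables. If no early event is lost, the correction does no harm.
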